### 3.2.3.3. Imputation for Intercurrent Events of Discontinuation due to AE or Lack of Efficacy

For patients with intercurrent events of discontinuation due to adverse event OR due to lack of efficacy, imputation will follow the same strategy as above, with the difference that the imputed Week 24 values (after following the steps in the section above) will be adjusted and therefore ascribed an extreme unfavourable value.

Specifically, for these patients who discontinued due to adverse event or due to lack of efficacy at Week 24, the missing values will be scaled to "worse" as compared to patients with MAR Week 24 data. Ie, a scalar value of 10% worsening, using a patient's baseline to define the 10% scalar value, will be added to the patients Week 24 imputed value in order to 'worsen' the outcome.

The scalar will be determined as follows. Patients are expected to have an average ADAS Cog 11 score of ~25, and thus a 10% worsening would average approximately 2.5 points. Worsening of 2.5 points in the ADAS-Cog 11 was similar for the placebo arms in those clinical trials for many approved drugs (eg, donepezil, rivastigmine, memantine), and thus 10% of a patient's baseline value is a clinically relevant and meaningful adjustment (worsening) to the patients who discontinued due to adverse event or due to lack of efficacy.

For example, assume a patient discontinues prematurely due to an adverse event and the patient is therefore missing the Week 24 ADAS Cog 11 value. Imputation of missing values for this patient will be performed as follows:

- The patients missing values after discontinuation will *FIRST* be imputed accorded to the same procedures as for all patients with missing values.
- Then, the Week 24 imputed value will be *FURTHER* scaled (worsened) as follows:
  - The patients baseline value for the variable will be identified (eg, assume the patient has an ADAS Cog 11 score of 27 at baseline). And note that increases in the ADAS Cog-11 indicate a worsening of function, and thus increases from baseline would indicate a poor treatment outcome.
  - The baseline score will be multiplied by 10%, eg,  $27 * 0.1 = 2.7$ . This 2.7 would be this individual patients' scalar adjustment to the Week 24 ADAS Cog 11 score.
  - Therefore, the imputed Week 24 score for that patient will be *increased (worsened) by 2.7*. Thus, if, for example, the patients Week 24 value is imputed by the primary imputation methods to be 25, *a further scalar increase of 2.7 will be attributed for that patient*, ie, the resulting imputed score for analysis for that patient will be  $25+2.7 = 27.7$ .

Thus, in this manner, patients who discontinue due to adverse event or due to lack of efficacy will, as a group, have a worse distributional outcome for each co-primary endpoint than other patients with missing values at random. A 10% worsening in the co-primary endpoints is considered sufficient to ensure that these patients who discontinued due to adverse event or due to lack of efficacy are treated accordingly with unfavorable outcomes.

**3.2.4. The population-level summary for the variable which provides, as required, a basis for a comparison between treatment conditions**

The population-level summary for the co-primary variables in this study are ADAS-Cog-11 score change from baseline to Week 24 and ADCS-ADL score change from baseline to Week 24. The basis for the comparison will be made using the Randomized population and the MMRM analysis on the imputed dataset that specifically attributes distributionally ‘worse’ outcomes to those patients with an intercurrent event of dropout due to either adverse event or lack of efficacy.

#### 4. ANALYSIS POPULATIONS

The Intent-to-Treat (ITT) Population was defined as:

- All subjects randomized to treatment who have taken at least one dose of double-blind investigational product and who have at least one baseline (and one post baseline) primary efficacy assessment for at least one of either the ADAS-Cog-11 or the ADCS-ADL. This will be the primary population used for the efficacy analysis.

Note that the inclusion of ‘and one post baseline’ assessment was added to the original definition.

The Randomized Population was defined as all patients who are randomized.

CHMP advice suggested the following:

- “With regard to the definition of the ITT population, it is considered that the Intention-To-Treat population, as the definition already suggests, should consist of all patients randomized and the Applicant will have to justify that their definition (all randomized who took medication with one post-baseline assessment) will lead to the same conclusions on treatment effects.”

Therefore, an analysis of the **Randomized Population** will be performed for the co-primary endpoints using the multiple imputation strategy as indicated above, and the responder analyses as described for those outcomes.

A comparison of the conclusions regarding treatment effect between the Randomized Population and the ITT population will be performed. This analysis comparison will allow for justification as to whether the ITT population (as defined) leads to the same conclusions from the Randomized population.

## 5. DESCRIPTIONS OF ADDITIONAL STATISTICAL ANALYSES

The key analysis method of these additional imputed data (as described in the previous sections) will be using the mixed model repeated measures (MMRM) approach. A summary of this method is described below.

Treatment comparisons between the intepirdine and placebo groups in ADAS-Cog-11 and ADCS-ADL change from baseline to Week 24 will be analyzed for the dataset using a mixed model for repeated measures with restricted maximum likelihood estimation, an unstructured covariance matrix, and the Kenward-Roger approximation for denominator degrees of freedom.

The same procedures for analysis of the imputed data (as were proposed in the original SAP) would then be performed, as follows:

- Each of the 100 imputed datasets will be analyzed using the MMRM model. The statistical model will be fitted with terms for treatment group, visit, treatment by visit interaction, baseline score, baseline MMSE, baseline score by visit interaction, and Region. In this way, the test of the efficacy endpoint at Week 24 will be obtained once for each of the 100 imputed datasets.
- The 100 resulting treatment effect parameters and standard errors from these will be combined to provide a distribution of parameters (and standard errors) upon which the sensitivity analysis will be concluded. PROC MIANALYZE will be used for this summary of the analysis.

Inferences will be drawn from treatment differences for the changes from baseline derived from the MMRM models at Week 24. As additional supportive information, treatment differences for each post baseline visit will also be derived. The estimated treatment difference for “intepirdine 35mg – Placebo” at each visit will be displayed in the summary of statistical analysis together with the 95% confidence interval and the associated p-value.

Least Squares Means for each visit will also be presented with the standard error and the number of subjects contributing to the Least Squares Means. Least Squares Means and estimated treatment differences for each visit and the associated 95% confidence interval will be displayed graphically.

Note that while the primary determination of the effects of treatment will remain based on the indicated analyses in the final SAP (August 9, 2017), comparison of those outcomes to the additional analyses above will be made to assess the robustness of the outcomes.

### 5.1. Sensitivity Analyses of the Primary Efficacy Results

CHMP as the following advice:

- “An appropriate primary analysis should be accompanied with sensitivity analysis to test assumptions on properties of methods and data. It is noted that the set of analyses defined in the SAP partly address a different target of estimation (alternative analysis methods termed “Sensitivity Analyses of the Primary Efficacy Results” in section 8.3.2.2. on observed cases). Single imputation methods as in “Sensitivity Analysis from Imputation of Missing Efficacy Data for Primary Efficacy Endpoints” (section 8.3.2.4.) would not be acceptable and the outlined analysis that makes use of multiple

imputation methods uses the complete trial population to make covariate based predictions for imputation. While multiple imputation methods are considered appropriate, the dataset used to generate imputations would have to be justified.”

In response to this advice, the following sensitivity analysis will be performed for the co-primary efficacy endpoints using the 100 imputed datasets:

- Analysis using a non-parametric (distribution-free) Wilcoxon Rank Sum Test of the treatment differences will be run for the Week 24 data, and conclusions will be based on the combined outcomes from the 100 imputed datasets. *Sample* SAS code is as follows. The actual SAS code may be modified as appropriate.

```
Proc nparlway data=dat;
  Class treat;
  Var outcome;
  ods select WilcoxonScores;
Run;
```

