10.2. Sample Size Considerations

The primary comparisons of interest are to compare RVT-101 to placebo at Week 24 for change from baseline in both ADAS-Cog-11 and ADCS-ADL. A sample size of 435 subjects per treatment group will allow a difference of 1.6 points between placebo and active treatment in the change from baseline in ADAS-Cog score to be detected with 95% power and a 0.05 significance level assuming an underlying standard deviation (SD) of 6.5.

This sample size will also allow a difference of 2 points between placebo and active treatment in the change from baseline in ADCS-ADL score to be detected with 90% power and a 0.05 significance level assuming an underlying SD of 9. Sample size estimates were based on data from study AZ3110866.

Both endpoints need to achieve a significance level of 0.05 to maintain an overall 5% significance level. Hence, the multiplicity issue associated with the trial having 2 primary endpoints is addressed as efficacy will only be concluded if both endpoints are significant.

Assuming a drop-out and missing data rate of approximately 25% up to Week 24, a total of approximately 1150 subjects will be randomized in a 1:1 ratio to RVT-101 or placebo.

The impact of baseline severity and possible sub-populations of milder and more moderate subjects is an important consideration of this study. Hence, a stratified randomization will be used to enroll subjects according to their baseline MMSE score in the groupings of 10-15 points, 16-20 points, and 21-26 points.

Two subgroups using MMSE score at baseline will be examined: moderate 10-20 and mild 16-26. The thresholds for randomization presented in [Table 4](#) will be enforced.

Table 4. Baseline Mini Mental State Examination Stratification

Baseline MMSE Score	10-15	16-20	21-26
Target for recruited population	≤30%; ≥20%	≤60%; ≥40%	≤30%; ≥20%

The purpose of this ratio is to ensure that approximately 70% of the recruited population will contribute data to a data-defined subgroup analysis of either milder or more moderate subjects on ADAS-Cog-11 and/or ADCS-ADL. It is estimated that a difference from placebo of 1.6 points in ADAS-Cog-11 and 2.0 points in ADCS-ADL will be observable with approximately 80% power in a subgroup, which includes approximately 70% of subjects.

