10.4. Key Elements of Analysis Plan

All hypothesis tests and confidence intervals will be 2-sided at an alpha level of 5%.

For statistical analysis, center information will be pooled by geographical region or size. The method of grouping by center will be agreed upon prior to unblinding the study and outlined in the Statistical Analysis Plan (SAP).

All efficacy and safety measures over the course of the study will be presented. Continuous data will be summarized by means, SDs, medians, maximum, minimum, and number of subjects. Categorical data will be summarized by counts and percentages.

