#### 3.2.2. Variable (or endpoint), to be obtained for each patient, that is required to address the scientific question

The co-primary endpoints to be obtained for each patient in this study to address the scientific question are ADAS-Cog-11 score at Week 24 and ADCS-ADL score at Week 24.

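### SAP 5.1 does not say whether its Wilcoxon test ranks Week 24 scores or change from baseline; ranking raw scores would weaken this supportive check

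*SAP*

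**What the plan says.** SAP 5.1 answers the regulator's request for sensitivity analyses with one test: a Wilcoxon rank-sum comparison of the arms at Week 24, run in each imputed dataset for both co-primary endpoints. On combining the results it says only that "conclusions will be based on the combined outcomes from the 100 imputed datasets". The sample code has a treatment class and a placeholder response variable. It has no baseline term and no strata, prints only the rank-score table, and is described as open to modification.

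The documents name the endpoint in two ways, although neither statement is about the Wilcoxon itself:

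- SAP 3.2.2, the estimand variable: "ADAS-Cog-11 score at Week 24 and ADCS-ADL score at Week 24".
- SAP 3.2.4, the population-level summary: "ADAS-Cog-11 score change from baseline to Week 24 and ADCS-ADL score change from baseline to Week 24". Protocol section 4 and SAP 5 (the MMRM) also use change from baseline.

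The imputation in SAP 3.2.3.2 works on the score at each visit. The worked example in 3.2.3.3 ends in a score (25 + 2.7 = 27.7), not a change.

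On randomisation, Protocol 10.2 says "a stratified randomization will be used to enroll subjects according to their baseline MMSE score", in groups 10-15, 16-20 and 21-26. The MMRM in SAP 5 includes baseline score, baseline MMSE, baseline score by visit, and region.

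**The concern.** In a model with baseline score as a covariate, analysing the Week 24 score or the change gives the same treatment difference. The loose wording therefore does no harm in the MMRM. A two-sample rank test has no such protection. If it ranks raw scores, differences in severity between patients stay in the noise. If it ranks change, subtracting baseline removes much of that noise.

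SAP 5 compares the added analyses with the primary results to judge robustness. If the primary MMRM is positive and the Wilcoxon is not, the reader has to know whether the result is fragile or the test was weak. The programmer also has no stated rule for turning 100 rank tests into one conclusion. Both choices could be made after unblinding, although SAP 1 gives agreement before unblinding as the aim.

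**Working it through.** **Inputs from the documents.** Protocol 10.2: "A sample size of 435 subjects per treatment group will allow a difference of 1.6 points between placebo and active treatment" on ADAS-Cog, "to be detected with 95% power and a 0.05 significance level assuming an underlying standard deviation (SD) of 6.5". For ADCS-ADL: "This sample size will also allow a difference of 2 points between placebo and active treatment", at 90% power with SD 9. Tests are two-sided at 5% (Protocol 10.4). Protocol 10.2.1 shows that these SDs are for change from baseline (observed 6.13 to 6.37 for ADAS-Cog and 8.84 to 9.36 for ADCS-ADL).

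**Assumed inputs.** The documents give no SD for raw Week 24 scores. The ranges used are 8 to 12 for ADAS-Cog-11 and 10 to 16 for ADCS-ADL.

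**Step 1: reproduce the plan's power.** Power = Φ(δ / (σ√(2/n)) − 1.96).

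- ADAS-Cog-11: 6.5 × √(2/435) = 0.4407; 1.6/0.4407 = 3.630; Φ(1.670) = 95.3%. Table 5 gives 95.2%.
- ADCS-ADL: 9 × √(2/435) = 0.6103; 2/0.6103 = 3.277; Φ(1.317) = 90.6%. Table 5 gives 90.6%.

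**Step 2: Wilcoxon on change.** For normal data the rank-sum test has relative efficiency 3/π = 0.955, so the effective n is 435 × 0.955 = 415.4.

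- ADAS-Cog-11: 6.5 × √(2/415.4) = 0.4510; 1.6/0.4510 = 3.548; Φ(1.588) = 94.4%.
- ADCS-ADL: 9 × √(2/415.4) = 0.6245; 2/0.6245 = 3.203; Φ(1.243) = 89.3%.

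The loss against the t-test is about 1 point.

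**Step 3: Wilcoxon on raw score.** Same formula, with the assumed raw SD in place of the change SD.

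| Endpoint (difference) | Assumed raw SD | Power |
|---|---|---|
| ADAS-Cog-11 (1.6) | 8 / 10 / 12 | 82% / 64% / 49% |
| ADCS-ADL (2.0) | 10 / 12 / 14 / 16 | 82% / 67% / 54% / 44% |

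If the SD is the same at baseline and Week 24, the variance of change is 2s²(1 − ρ), where s is the raw SD and ρ the correlation between the two visits. Ranking raw scores then loses power whenever ρ exceeds 0.5. The assumed ADAS-Cog SDs of 8 to 12 imply ρ = 1 − 6.5²/(2s²), or 0.67 to 0.85.

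**Step 4: simulation.** 3,000 trials at 435 per arm, with normal data, equal SDs at both visits, and an assumed correlation of MMSE with baseline score of 0.7 (ADAS-Cog) or 0.5 (ADCS-ADL). ANCOVA on baseline score and MMSE stands in for the MMRM.

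| Scenario (raw SD) | Wilcoxon, change | Stratified, change | Wilcoxon, raw | Stratified, raw | ANCOVA significant, raw Wilcoxon not |
|---|---|---|---|---|---|
| ADAS-Cog 8 | 94.2% | 95.6% | 82.4% | 88.6% | 15.6% |
| ADAS-Cog 10 | 94.7% | 95.6% | 64.7% | 76.5% | 32.6% |
| ADAS-Cog 12 | 94.7% | 95.4% | 49.0% | 61.4% | 48.5% |
| ADCS-ADL 11 | 89.8% | 90.6% | 73.2% | 77.1% | 22.6% |
| ADCS-ADL 13 | 88.9% | 89.5% | 60.8% | 67.4% | 33.8% |
| ADCS-ADL 15 | 89.5% | 90.5% | 48.9% | 53.6% | 44.8% |

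When change is ranked, the same discordance with ANCOVA is about 3% to 6%. Stratifying by MMSE adds about 1 point on change. A separate ADAS-Cog simulation at 512 per arm showed no gain (97.3% with and without strata). Stratifying does not rescue the raw-score test.

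**Step 5: imputed-data setting.** Take all 575 per arm and dilute the effect by the 11% dropout ceiling in SAP 3.2.3.1. Wilcoxon power on change is then about 95% (ADAS-Cog) and 91% (ADCS-ADL). On raw score it is about 66% (ADAS-Cog, SD 10) and 69% (ADCS-ADL, SD 12).

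**Step 6: pooling.** SAP 5 names PROC MIANALYZE only for the MMRM estimates and standard errors. A standardised statistic can be derived from the rank-score table, but 5.1 does not say that this will be done or how the 100 values will be combined.

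**The case against.** The strongest reply is that change from baseline is the natural reading. Section 5.1 concerns the co-primary endpoints, which Protocol section 4 lists as changes. SAP 2.1 pairs the MMRM and the Wilcoxon on the same endpoints, and the MMRM analyses change. SAP 5 itself speaks of the endpoint at Week 24 when it means that change analysis. The code is a sample with placeholder names. The addendum describes additions to a final SAP that is not available here and may settle the matter. All of this stands, and on that reading the power problem nearly disappears.

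It makes change the likelier reading without fixing it. SAP 3.2.2 says score, the imputed values are scores, and 5.1 mentions no subtraction of baseline.

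Three stronger readings might be inferred, and the documents support none of them:

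- *The SAP defines the Wilcoxon outcome in two conflicting ways.* It does not. The mismatch is in the estimand text; the addendum leaves the Wilcoxon outcome undefined.
- *Leaving out the MMSE strata makes the test weak.* On change scores this costs about 0 to 1 point of power.
- *A failed Wilcoxon could undo a co-primary result.* SAP 5 leaves the primary determination with the final SAP.

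**Conclusion.** The ranked variable and the pooling rule are not fixed in the addendum. If change is ranked, power at 435 per arm is about 94% (ADAS-Cog-11) and 89% (ADCS-ADL), close to the plan's own figures. If raw scores are ranked, it is about 82% to 49% and 82% to 44% over the assumed SD ranges, and disagreement with a baseline-adjusted analysis becomes common.

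The size of the loss rests on the assumed raw SDs, normal data and the planned effects. Its direction needs only a raw SD larger than the change SD. The harm is a possibly misleading robustness statement, with no effect on the primary inference. This is a minor point about a supportive analysis, and it falls away to the extent that the final SAP already defines the outcome and the pooling.

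**What to change.** Before unblinding:

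1. State in SAP 5.1 that the Wilcoxon ranks change from baseline to Week 24, calculated in each imputed dataset after any worsening adjustment.
2. Make SAP 3.2.2 agree with 3.2.4 by naming change from baseline.
3. Stratify by the three MMSE randomisation groups (van Elteren). The gain is small, about 0 to 1 point, but the test then matches the randomisation.
4. State the pooling rule. Take the standardised statistic z from each of the 100 datasets. Use the mean z as the estimate, with total variance 1 + (1 + 1/100)B, where B is the between-imputation variance of z, and refer the ratio of mean z to the root of that variance to Rubin's t distribution. Amend the sample code to output z.

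The cost is a few lines of text and code. No new data are needed, and the primary analysis does not change. If the final SAP already covers items 1, 3 or 4, a cross-reference is enough.

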## 5.2. Responder Analyses

CHMP had the following advice:

- “The defined responder analyses should not only be based on observed cases with assessments at week 24. Imputations should be used and an approach with missing data imputed as failures should be included. A responder criterion of 4 on the ADAS-Cog 11 should be generally implemented in addition to improvement of at least 3 points.”

The analyses of responder (defined below) are consistent with that advice, as shown below.

The responder analyses will be performed based on the observed data (subjects with Week 24 assessment for the endpoint of interest), *as well as analyzed assuming all subjects with missing Week 24 are treatment failures (non-responder)*.

The following responder definitions will be defined and each will be analyzed using a logistic regression model as described above as well as a CMH test. The percentage of responders and the difference in proportions compared to placebo will be presented. This analysis is planned for both the ITT population as currently defined as well as the Randomized population.

1. ***ADAS-Cog-11 Improvement by at least 3 points at Week 24***
  - a. ***Repeated for by at least 4 points at Week 24***
  - b. Repeated for ‘no change or improvement’ vs ‘worsening’
2. ADAS-Cog-11 No change/improvement vs worsening at Week 24
3. CIBIC+ No change/improvement vs worsening at Week 24
4. ADAS-Cog-11/CIBIC+/ADAS-Cog-11 composite, simultaneously meeting the criteria for:
  - a. ADAS-Cog-11 Improvement of at least 3 points at Week 24
  - b. CIBIC+ No change/improvement at Week 24

- c. ADCS-ADL No change/improvement at Week 24
- 5. ADAS-Cog-11/ADCS-ADL composite, simultaneously meeting the criteria for:
  - a. ADAS-Cog-11 Improvement by at least 3 points at Week 24
  - b. ADCS-ADL No change/improvement at Week 24
- 6. ADAS-Cog-11/CIBIC+/ADCS-ADL composite, simultaneously meeting the criteria for:
  - a. ADAS-Cog-11 Improvement of at least 4 points at Week 24**
  - b. CIBIC+ No change/improvement at Week 24
  - c. ADCS-ADL No change/improvement at Week 24
- 7. ADAS-Cog-11/ADCS-ADL composite, simultaneously meeting the criteria for:
  - a. ADAS-Cog-11 Improvement by at least 4 points at Week 24**
  - b. ADCS-ADL No change/improvement at Week 24

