10.4.4. Responder Analysis

In this trial the following responder definitions will be presented:

1. ADAS-Cog-11: Improvement by at least 3 points from baseline at Week 24
2. ADCS-ADL: No change or improvement from baseline at Week 24
3. CIBIC+: No change or improvement at Week 24
4. ADAS-Cog-11 composite: Simultaneously meeting the criteria for ADAS-Cog-11, CIBIC+, and ADCS-ADL

Alternative composite endpoints and definitions of responders may be explored. The percentage of responders and the difference in proportions compared to placebo will be presented. This data will be analyzed using logistic regression or Cochran–Mantel–Haenszel test. Further details will be given in the SAP.

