## **2.1. Summary of Additions to Statistical Analysis Plan in Response to Scientific Advice**

The following is a summary of the additions to the SAP as well as explanation of the estimand and assumptions on missing data to the SAP.

1. A description of the estimand (based on ICH E9 R1 Addendum) is provided. A detailed description of intercurrent events is included (see [Section 3.2.3](#)).
2. A description of the estimated proportion of missing data due to overall dropout, due to missing at random and missing not at random reasons is provided (see [Section 3.2.3.1](#)).

In response to other comments in the CHMP scientific advice, the following additional analyses have been added.

1. Addition of a new imputation of missing data, using missing imputation methods as suggested by CHMP, is included. This new analysis will include:

- a. The data will be imputed assuming missing not at random data. This imputation method will use information from patients receiving placebo (but not from patients receiving Intepirdine) in order to avoid a potential overestimation of the treatment effect. See [Section 3.2.3.2](#).
  - b. For patients who discontinued due to adverse event or due to lack of efficacy, imputation is treated differently. Specifically, a scalar adjustment to the imputed values will be performed in order to assign an unfavourable outcome. See [Section 3.2.3.3](#).
2. These imputed datasets will be used to run additional analyses using the MMRM and Wilcoxon tests for the ADAS-Cog and ADCS-ADL endpoints at Week 24. The analysis of these endpoints (and the responder outcomes) will *also* be performed on the Randomized population (in addition to the already-planned ITT population), and a comparison of the outcomes between the ITT population and Randomized population outcomes will be performed. See [Section 4](#), [Section 5](#).

Further, for clarification, the responder analysis as was originally in the SAP is re-iterated to address the comment from CHMP regarding treating missing data as failures.

1. The responder analysis (as is included in the final SAP) is confirmed to be performed with missing data imputed as failure (as well as being performed with observed cases only). See [Section 5.2](#).

The following sections describe the additions to the SAP per the scientific advice.

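### SAP addendum 5.2, item 2 repeats item 1b, so the responder list has no stand-alone ADCS-ADL definition although protocol 10.4.4 specifies one (minor, wrong as written)

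*SAP*

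**What the plan says.** Protocol 10.4.4 gives four responder definitions at Week 24, in this order: ADAS-Cog-11 improved by 3 points or more; "ADCS-ADL: No change or improvement from baseline at Week 24"; CIBIC+ not worse; and a composite that requires all three. Protocol section 4 names the three-way composite as the responder endpoint among the secondary endpoints.

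SAP addendum 5.2 sets out its own numbered list. Item 1 is ADAS-Cog-11 improvement of at least 3 points, 1a repeats it at 4 points, and 1b repeats it as not worse versus worse. Item 2 then reads "ADAS-Cog-11 No change/improvement vs worsening at Week 24". Item 3 is CIBIC+. Item 4 is headed "ADAS-Cog-11/CIBIC+/ADAS-Cog-11 composite, simultaneously meeting the criteria for", followed by three criteria: one on ADAS-Cog-11, one on CIBIC+ and one on ADCS-ADL. Items 5 to 7 are further composites.

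On scope, 5.2 specifies an observed-case analysis and one that counts missing Week 24 data as failure. It adds that "This analysis is planned for both the ITT population as currently defined as well as the Randomized population" and that "each will be analyzed using a logistic regression model as described above as well as a CMH test". Addendum 2.1 describes the source of the list: "the responder analysis as was originally in the SAP is re-iterated to address the comment from CHMP".

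**The concern.** ADCS-ADL is one of the two co-primary endpoints, and protocol definition 2 is its only single-scale responder display. A programmer who works from addendum 5.2 would build the ADAS-Cog-11 not-worse responder twice and would not build the ADCS-ADL one. Neither 2.1 nor 5.2 announces that the ADCS-ADL responder has been withdrawn or explains why it would be. The list therefore disagrees with the protocol without saying so.

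The slip may also extend beyond the addendum. Section 2.1 presents the list as a restatement of the final SAP. Section 5.2 also points to a logistic model described above, and no such description appears anywhere in the addendum. Both suggest text carried over from the August 9, 2017 document, so the same error could be there.

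**Working it through.** There is no figure of the plan to reproduce. The check is a comparison of two lists and a count.

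**Step 1: entries in addendum 5.2.**

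| Entry | Scale(s) | Criterion |
|---|---|---|
| 1 | ADAS-Cog-11 | improved by 3 or more |
| 1a | ADAS-Cog-11 | improved by 4 or more |
| 1b | ADAS-Cog-11 | not worse |
| 2 | ADAS-Cog-11 | not worse |
| 3 | CIBIC+ | not worse |
| 4 | ADAS-Cog-11, CIBIC+, ADCS-ADL | improved by 3 or more; not worse; not worse |
| 5 | ADAS-Cog-11, ADCS-ADL | improved by 3 or more; not worse |
| 6 | ADAS-Cog-11, CIBIC+, ADCS-ADL | improved by 4 or more; not worse; not worse |
| 7 | ADAS-Cog-11, ADCS-ADL | improved by 4 or more; not worse |

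By type: 4 on ADAS-Cog-11 alone + 1 on CIBIC+ alone + 0 on ADCS-ADL alone + 4 composites = 9 entries. Rows 1b and 2 are identical, so 9 − 1 = 8 are distinct.

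**Step 2: mapping from protocol 10.4.4.** Definition 1 maps to item 1, definition 3 to item 3 and definition 4 to item 4. Definition 2 maps to nothing. So 3 of the 4 protocol definitions are present.

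**Step 3: which reading of item 2 was meant.** The protocol order is ADAS-Cog-11, ADCS-ADL, CIBIC+, composite, so item 2 sits where ADCS-ADL would be expected. The heading of item 4 names ADAS-Cog-11 twice, yet criterion 4c is on ADCS-ADL, and the parallel item 6 carries all three scale names correctly. The same scale name was substituted in both places. That item 2 was meant to be ADCS-ADL is an inference, but a strong one.

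**Step 4: results involved.** Each entry is planned with 2 missing-data rules × 2 populations × 2 methods = 8 results, so 9 × 8 = 72 are listed, of which 8 repeat item 1b. The 8 results that a stand-alone ADCS-ADL entry would have given divide as follows:

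- ITT: 1 population × 2 rules × 2 methods = 4. These may already be specified in the August 9, 2017 SAP.
- Randomized, observed cases: 1 × 1 × 2 = 2. By the ITT definition in addendum section 4, a randomized and dosed patient with baseline and Week 24 ADCS-ADL values is in the ITT population, so these would essentially repeat the ITT observed-case results.
- Randomized, missing as failure: 1 × 1 × 2 = 2. In the file, these depend on the addendum list alone.

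**Step 5: after correction.** With ADCS-ADL in item 2, all 9 entries are distinct and all 4 protocol definitions are covered.

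**The case against.** The strongest reply is that the addendum removes nothing. Its introduction and section 3.2.3.1 say that its analyses are additional to the final SAP, and protocol definition 2 still stands. A reader might infer that the ADCS-ADL responder has been dropped from the trial, or that all 8 results in step 4 are lost. The documents do not support either reading. Section 2.1 says that the responder analysis of the final SAP "is confirmed to be performed with missing data imputed as failure (as well as being performed with observed cases only"), and that SAP, which is not available here, may define the ADCS-ADL responder correctly for the ITT population. This part of the objection stands and limits the consequence. It does not remove the defect, because 5.2 states its own list and section 2.1 presents the Randomized-population responder run as new.

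A reader might also infer from the heading of item 4 that the composite itself is wrong. It is not: the criteria beneath it match protocol definition 4.

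Finally, a reader might conclude that 5.2 fails the CHMP advice it quotes, "Imputations should be used and an approach with missing data imputed as failures should be included", because the multiply imputed datasets are not used for responders. The text does not establish that. Section 2.1 assigns those datasets to the MMRM and Wilcoxon analyses of the two scales, 5.2 names two rules for responders, and section 2.1 itself calls the failure rule an imputation. Whether CHMP wanted more is arguable, and it is a separate matter from this slip.

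**Conclusion.** The defect is certain as a matter of text: item 2 equals item 1b, the list has 8 distinct definitions among 9 entries, and it contains no stand-alone ADCS-ADL responder. It is wrong as written, and minor.

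The size of the consequence is less certain. At least two results are not provided for: the Randomized population with missing counted as failure, by logistic regression and by CMH. The number rises to 8 only if the August 9, 2017 SAP carries the same slip and the near-duplicate observed-case results are counted. Which case applies cannot be settled from the file.

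ADCS-ADL is still analysed as a co-primary endpoint and still enters the composites in items 4 to 7. The co-primary tests, power, type I error and the three-way composite responder are unaffected. The heading of item 4 is an editorial error only.

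**What to change.** In addendum 5.2, replace the scale name in item 2 with ADCS-ADL and leave the rest of the item as it is. Change the heading of item 4 so that it names ADAS-Cog-11, CIBIC+ and ADCS-ADL, as the heading of item 6 does. Both changes bring the list into line with protocol 10.4.4. Before programming, check the corresponding items in the August 9, 2017 SAP and correct them if they carry the same slip.

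The program for item 2 must change direction as well as variable. A higher score is worse on ADAS-Cog-11 (protocol 8.3.1.2) and a lower score is worse on ADCS-ADL (protocol 8.3.1.3), so not worse means a change of 0 or below on the former and 0 or above on the latter.

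The cost is two wording corrections and one document check. The corrected item uses data already collected and replaces a duplicate, so the number of planned results does not increase.
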